### Primary endpoints

The primary endpoint of this study is the proportion of subjects with PSMA-positive (identified by H&E staining and immunohistochemistry) "dominant" PC lesion(s) greater than 5mm in diameter, whose lesion(s) have been successfully identified by  $^{89}\text{Zr}$ -df-IAB2M imaging. Because this is an exploratory pilot study, no formal sample size/power calculation is required. However, with a sample size of 20 patients in the study, a two-sided 95% confidence interval for the proportion of patients successfully imaged by  $^{89}\text{Zr}$ -df-IAB2M can be constructed to be within  $\pm 19.0\%$  of the observed proportion of patients with successful imaging by  $^{89}\text{Zr}$ -df-IAB2M. This calculation assumes an  $^{89}\text{Zr}$ -df-IAB2M imaging-success proportion of 75%. All estimates from the study will serve as preliminary data (i.e., hypothesis-generating) for future studies.

- Descriptive statistics will be calculated for the study cohort:
  - Median and inter-quartile range or mean and standard deviation for age, biopsy Gleason score (1o, 2o, Total), number of cores on biopsy, number of positive cores on biopsy, PSA, number of lesions on prostatectomy pathology (RP pathology), lesion size on RP pathology, Gleason score (1o, 2o, and total) on RP pathology.
- Lesion-based analysis:

- SUVmax measurements of Zr-df-IAB2M PET/CT images obtained in tumor and non-tumor regions will be compared. To account for inpatient correlation of multiple lesions, a linear mixed-effects model with a random intercept will be used to estimate and compare the mean SUVmax values in different regions.  $P < 0.05$  will be indicative of a significant difference as described by Turkbey B, et al.
- Positive and negative predictive values will be estimated by using generalized estimating equations (GEE) modeling, with logit link function and a working independence correlation structure. Robust variance estimation and the delta method will be used to calculate standard errors of the positive and negative predictive values. The Wald test with robust variance estimates will be used for statistical inference. Subgroup analyses will be performed for high, moderate, and low risk disease (see secondary endpoints).

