  - The Spearman-rank correlation coefficient will be used to evaluate the association between SUV and serum PSA levels obtained during screening.
- To determine the ability of *in vivo*  $^{89}\text{Zr}$ -df-IAB2M PET/CT to identify extra-prostatic extension:
  - The Wilcoxon rank-sum test will be used to compare  $\text{SUV}_{\text{max}}$  measurements of IAB2M-positive extra-prostatic sites between lesions with and without histopathologically confirmed extra-prostatic extension.
- To determine the ability of *in vivo*  $^{89}\text{Zr}$ -df-IAB2M PET/CT to identify occult lymph node involvement:

- The Wilcoxon rank-sum test will be used to compare  $SUV_{max}$  measurements of IAb2M-positive lymph nodes between patients with and without histopathologically confirmed lymph node involvement.
- To further evaluate the safety of  $^{89}Zr$ -DF-IAB2M PET/CT and  $^{68}Ga$ -PSMA-HBED-CC imaging.
  - See section on Risks

Additionally, we will assess whether there is improved sensitivity in detecting localized PCa by combining imaging results. This assessment will be done by estimating the PPV with different combinations of imaging modalities. The incremental effect of an additional imaging modality on PPV will be tested with the Wald test, as described by Turkbey B, et al.

All p-values will be two-sided with statistical significance evaluated at the 0.05 alpha level. All analyses will be performed in SAS Version 9.4 (SAS Institute, Inc., Cary, NC) and Stata Version 13.0 (StataCorp, College Station, TX).

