## 12.2 Sample Size/Accrual Rate

The sample size for this study will be 20 patients. We anticipate an accrual rate of at least two patients per month. With a sample size of 20 patients in the study, a two-sided 95% confidence interval for the proportion of patients successfully imaged by  $^{89}Zr$ -df-IAB2M can be constructed to be within  $\pm 19.0\%$  of the observed proportion of patients with successful imaging by  $^{89}Zr$ -df-IAB2M. This calculation assumes an  $^{89}Zr$ -df-IAB2M imaging-success proportion of 75%. All estimates from the study will serve as preliminary data (i.e., hypothesis-generating) for future studies.”

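### PPV and NPV inference relies on a robust variance and delta-method Wald approach with no small-sample provision for at most 20 patients, and gives a standard error of zero at 100%

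*Combined protocol and SAP*

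**What the plan says.** The lesion-based analysis in Section 12.1 (under Primary endpoints) estimates PPV and NPV by GEE with a logit link and working independence. It then says: "Robust variance estimation and the delta method will be used to calculate standard errors of the positive and negative predictive values". The next sentence reads: "The Wald test with robust variance estimates will be used for statistical inference". It adds: "Subgroup analyses will be performed for high, moderate, and low risk disease", and refers the reader to the secondary endpoints for these groups, but no risk groups are defined there and no subgroup sizes are given.

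The Secondary endpoints text uses the same kind of test for combinations of modalities: "The incremental effect of an additional imaging modality on PPV will be tested with the Wald test". It also sets a threshold: "All p-values will be two-sided with statistical significance evaluated at the 0.05 alpha level".

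On size, Section 12.2 states: "The sample size for this study will be 20 patients". The only precision figure in the plan is for the primary endpoint: "a two-sided 95% confidence interval for the proportion of patients successfully imaged by" the tracer, within ±19.0% at an assumed success proportion of 75%. No precision is stated for PPV or NPV. Section 12 names no small-sample correction to the robust variance, no t reference, no exact alternative, and no rule for an estimate of 0% or 100%. Sections 12.1 and 12.2 describe all estimates as preliminary and hypothesis-generating.

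**The concern.** The robust variance is justified when there are many independent clusters. Here the cluster is the patient, and 20 is the ceiling: PPV uses only patients with at least one PET-positive finding, and each risk subgroup uses fewer again. With few clusters the robust standard error tends to be too small, and a normal reference ignores the uncertainty in it.

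The delta method adds a second weakness. It puts a symmetric error on the probability scale, where the approximation is poorest near 0 or 1. If every focus in a group is a true positive, the logit estimate is infinite and the probability-scale standard error is exactly zero.

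What is at stake is the stated uncertainty of PPV, NPV, the subgroup results and the incremental-PPV test. These estimates are meant to feed future studies, so error bars that are too small would be carried into a later design.

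**Working it through.** **Inputs from the documents.** 20 patients; two-sided 95% confidence and alpha 0.05; GEE with logit link and working independence; robust variance, delta method and Wald test; three risk groups of unstated size.

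**Assumptions not in the documents.** 1 + Poisson(1) foci per patient (mean 2); beta-binomial outcomes with intra-patient correlation 0 to 0.2; true PPV 0.75 or 0.90; 7 or 5 patients per subgroup. Three groups sharing 20 patients average 20/3 ≈ 7.

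**The plan's own figure.** 1.96 × √(0.75 × 0.25 / 20) = 1.96 × 0.0968 = 0.190. The ±19.0% for the primary endpoint reproduces. It is also a Wald half-width, but for a different quantity.

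**Planned method for PPV.** Let patient i have m_i positive foci, of which y_i are true positives, and let N = Σ m_i. The GEE estimate is p̂ = Σ y_i / N. The robust variance carried to the probability scale by the delta method gives

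SE = √( Σ (y_i − m_i p̂)² ) / N, with literal interval p̂ ± 1.96 × SE.

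Coverage of the nominal 95% interval from 20,000 simulated trials per setting, with boundary results counted as misses:

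| Patients | Coverage, PPV 0.75 | Coverage, PPV 0.90 | Results at 0% or 100%, PPV 0.90 |
|---|---|---|---|
| 20 | 91-92% | 87-90% | about 2-3% |
| 7 (assumed) | 83-85% | about 70-74% | about 24-28% |
| 5 (assumed) | 81-84% | about 58-61% | about 36-41% |

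At PPV 0.75 the mean robust SE is about 95% of the true standard deviation with 20 patients, 85-87% with 7 and 78-80% with 5.

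**The boundary.** If y_i = m_i for every patient, then p̂ = 1, every term in the sum is zero, and SE = 0. The reported interval runs from 100% to 100%. With one focus per patient, the exact (Clopper-Pearson) 95% lower limit for n out of n is 0.025^(1/n):

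- 20/20: 83.2%
- 7/7: 59.0%
- 5/5: 47.8%

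**What a correction does to single estimates.** With 20 patients, a back-transformed logit interval with the Kauermann-Carroll correction and t on 19 df covers 96-98% away from the boundary. If boundary results count as misses, it covers about 94-96% for PPV 0.75 to 0.90. It is still undefined at 0% or 100%, so it does not replace a boundary rule.

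**What the logit scale does to the incremental-PPV test.** This was simulated under no true increment. Assumed: 20 patients, 2 to 3 positive foci per patient on average, correlation 0.1 to 0.3, the second modality keeping 70% of positives regardless of truth, and boundary results excluded. Type I error at nominal 5%:

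- Probability-scale Wald, uncorrected: 5-9%.
- Probability scale, corrected variance and t: 2-5%.
- Logit scale, corrected variance and t: 5-8% at PPV 0.70-0.75, 7-12% at 0.80, and 19-32% at 0.90.

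The logit scale therefore suits intervals for a single PPV but not the test of a difference between two PPVs from the same patients.

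NPV was not simulated, because the number of negative units per patient is not given.

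**The case against.** The strongest defence is that the plan names standard errors and a Wald test but never says how an interval for PPV or NPV is formed. The model has a logit link, so the interval could be built on the logit coefficient. A plain logit Wald interval with 20 patients covers about 94-96% away from the boundary, close to nominal. The absence of a correction is likewise read from silence; the plan does not exclude one. A reader might therefore infer that the planned intervals are simply wrong, and the documents do not support that. They support a narrower statement: the method is underspecified and performs poorly if its delta-method wording is followed literally. That wording does point to the probability scale, and the logit alternative still fails at 100%.

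A reader might also infer that each risk group will hold 5 to 7 patients. The documents do not say so. The groups are undefined and might be lesion-level, in which case one patient could contribute to several. The subgroup figures are illustrations.

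Finally, the analysis is exploratory, no decision rule uses PPV, and the primary endpoint is a patient-level proportion to which none of this applies. That limits the consequence. It does not remove the point, because the plan attaches p-values at 0.05 and intends the estimates as preliminary data for later studies.

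**Conclusion.** The point holds as a weakness of a secondary analysis. Under the literal reading and the stated assumptions, the full-cohort PPV interval falls short of 95% by about 3-4 points at PPV 0.75 (95 − 92 to 95 − 91) and 5-8 points at 0.90 (95 − 90 to 95 − 87). That is modest. The failure is serious if subgroups are as small as 5 to 7 patients: coverage is about 81-85% at PPV 0.75, and at PPV 0.90 about 24-41% of results would carry a standard error of zero. A result of 7/7 would be reported with no uncertainty, although the exact lower limit is 59%.

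The uncorrected incremental-PPV test is mildly liberal at worst (5-9% against 5%) under its own assumptions. NPV shares the structure, but no size can be attached to it. The primary endpoint and its ±19.0% are untouched.

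**What to change.** Amend Section 12.1 as follows:

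- **Single PPV and NPV estimates:** form the interval on the logit scale and back-transform, using a small-sample-corrected robust variance (Kauermann-Carroll or Mancl-DeRouen) and a t reference on (patients − 1) degrees of freedom, counting the patients who contribute.
- **Incremental-PPV test:** keep the difference on the probability scale with the corrected variance and t reference. Do not move this test to the logit scale.
- **Any estimate of 0% or 100%:** report a pre-specified exact interval with the patient as the unit, since neither the logit scale nor the variance correction helps there.
- **Risk subgroups:** define them, then report counts and patient-level proportions without Wald p-values.

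The cost is a few sentences and a modest amount of programming, with no new data or patients. Intervals become somewhat wider, and the subgroup p-values are given up.

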### Secondary endpoints

- To determine the ability of *in vivo* Zr-df-IAb2M PET/CT to correlate with pathological features (i.e. Gleason pattern, diameter and PSMA-positivity):
  - The Wilcoxon rank sum test will be used to compare lesions that were and were not identified on *in vivo* PET with respect to lesion size, immunohistochemical PSMA staining, and Gleason score (demonstrated by histopathology). This lesion based analysis will be performed in a similar fashion as described above.
- To compare the *in vivo* Zr-df-IAb2M PET/CT and Ga-PSMA-HBED-CC PET/CT to *in vivo* mpMRI:
  - The diagnostic accuracy of Zr-df-IAB2M PET/CT and Ga-PSMA-HBED-CC PET/CT imaging in patients with prostate cancer will be compared with that of mpMRI imaging by using sector-based analysis, as described by Turkbey B et al. The estimates of patient-specific sensitivity and specificity will be defined as the proportion of true-positive sectors and the proportion of true-negative sectors in each patient. Overall sensitivity and specificity will then be estimated by calculating the mean (and standard error) of these individual-

specific estimates across patients. Differences in sensitivity and specificity between modalities will then be evaluated by the Wilcoxon signed-rank test.

- To determine the sensitivity, specificity, PPV, NPV of IAB2M to detect all pathologically identified PCa lesions that do not meet criteria for clinical significance (defined as:  $< 0.5 \text{ cm}^3$  with Gleason pattern  $< 4$ ):
  - As above, but for lesions considered not to be clinically significant.
- To correlate IAB2M positivity (SUV) and lesion size:
  - The Spearman-rank correlation coefficient will be used to evaluate the association between SUV and size of the lesion (procedure for size measurements are defined in Section 9.1.3).
- To correlate IAB2M positivity (SUV) and Gleason pattern (3, 4 and 5):
  - The Spearman-rank correlation coefficient will be used to evaluate the association between correlate SUV and the histopathologically defined Gleason pattern. The Wilcoxon rank-sum test will also be used to compare  $\text{SUV}_{\text{max}}$  measurements between lesions with low Gleason score (3+4 or lower) and high Gleason score (4+3 or higher).
- To correlate IAB2M positivity (SUV) and PSA:
  - The Spearman-rank correlation coefficient will be used to evaluate the association between SUV and serum PSA levels obtained during screening.
- To determine the ability of *in vivo*  $^{89}\text{Zr}$ -df-IAB2M PET/CT to identify extra-prostatic extension:
  - The Wilcoxon rank-sum test will be used to compare  $\text{SUV}_{\text{max}}$  measurements of IAB2M-positive extra-prostatic sites between lesions with and without histopathologically confirmed extra-prostatic extension.
- To determine the ability of *in vivo*  $^{89}\text{Zr}$ -df-IAB2M PET/CT to identify occult lymph node involvement:

- The Wilcoxon rank-sum test will be used to compare  $SUV_{max}$  measurements of IAb2M-positive lymph nodes between patients with and without histopathologically confirmed lymph node involvement.
- To further evaluate the safety of  $^{89}Zr$ -DF-IAB2M PET/CT and  $^{68}Ga$ -PSMA-HBED-CC imaging.
  - See section on Risks

Additionally, we will assess whether there is improved sensitivity in detecting localized PCa by combining imaging results. This assessment will be done by estimating the PPV with different combinations of imaging modalities. The incremental effect of an additional imaging modality on PPV will be tested with the Wald test, as described by Turkbey B, et al.

All p-values will be two-sided with statistical significance evaluated at the 0.05 alpha level. All analyses will be performed in SAS Version 9.4 (SAS Institute, Inc., Cary, NC) and Stata Version 13.0 (StataCorp, College Station, TX).

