### Prostate Specific Membrane Antigen (PSMA)

PSMA is the single, most well-established, highly restricted prostate epithelial cell membrane antigen known. Although first thought to be entirely prostate-specific, subsequent studies demonstrated that PSMA is also expressed by some brain astrocytes and cells of the small intestine, proximal renal tubules and salivary glands. However, the level of expression in these non-prostate tissues is between a hundred-fold to a thousand-fold less than in prostate tissue and the site of PSMA expression in these normal cells (brush border/luminal location) are not readily accessible to circulating antibodies because of the blood: brain barrier or, in the case of the epithelial locations, due to intervening cell layers, basement membrane and epithelial tight junctions.

In contrast to other well-known prostate-restricted molecules such as PSA and prostatic acid phosphatase (PAP), which are secretory proteins, PSMA is a type II integral cell-surface membrane protein that is not secreted. Pathology studies indicate that PSMA is expressed by virtually all prostate cancers and PSMA expression increases progressively in higher grade cancers, metastatic disease, and hormone-refractory prostate cancer. These qualities make PSMA an ideal target for monoclonal antibody (mAb) imaging and/or therapy.

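### SUV and PET detection are related to Gleason grade without accounting for lesion size, so the planned tests cannot show whether uptake tracks grade beyond size

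*Combined protocol and SAP*

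**What the plan says.** Section 12.1 (Secondary endpoints) relates uptake to grade in three ways:

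- SUV across the three Gleason patterns: "The Spearman-rank correlation coefficient will be used to evaluate the association between correlate SUV and the histopathologically defined Gleason pattern".
- SUVmax in lesions scored 3+4 or lower against lesions scored 4+3 or higher, by a Wilcoxon rank-sum test.
- Detection: "The Wilcoxon rank sum test will be used to compare lesions that were and were not identified" on PET, with size, PSMA staining and Gleason score each compared in turn.

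Lesion size has its own entry: "The Spearman-rank correlation coefficient will be used to evaluate the association between SUV and size of the lesion". Section 1.2 likewise lists size, Gleason pattern and PSA side by side as correlates of SUV. Neither section states an expected direction for size.

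The primary-endpoint part of Section 12.1 contains a random-intercept mixed model for SUVmax in tumor against non-tumor regions and a logit GEE for predictive values. Neither has a size covariate. Section 9.1.4.1 has the pathologist annotate size and Gleason score for each focus, and Section 9.1.2.1 records both SUVmax and SUVmean.

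The background in Section 2.1 says that "PSMA expression increases progressively in higher grade cancers". On testing, Section 12.1 says: "All p-values will be two-sided with statistical significance evaluated at the 0.05 alpha level". Sections 12.1 and 12.2 describe all estimates as preliminary and hypothesis-generating.

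**The concern.** Size can produce an association between SUV and grade if two things hold: measured SUV rises with lesion size, and larger foci tend to be of higher grade. The first is plausible from how SUVmax is formed. It is a maximum over voxels, so a lesion with more voxels has a higher expected maximum at the same tracer concentration. The second is plausible, but the documents neither state nor quantify it.

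If both hold, each of the three Gleason analyses will tend to show uptake or detection rising with grade even when uptake has no relation to grade among lesions of equal size. The background on PSMA expression points in the same direction, so such a result could easily be read as confirmation. The estimates are meant to inform later studies, and a size effect carried forward as a grade effect would mislead their design.

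**Working it through.** **The plan's own figure.** The only design calculation concerns the primary endpoint. "The sample size for this study will be 20 patients", and "a two-sided 95% confidence interval for the proportion of patients successfully imaged by" the tracer is said to lie within ±19.0 points at an assumed "imaging-success proportion of 75"%. Check: 1.96 × √(0.75 × 0.25 / 20) = 0.190. The figure reproduces. It does not bear on the Gleason analyses, for which the plan gives no lesion count, expected correlation or precision.

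**Is size handled elsewhere?**

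- The detection entry says that the lesion analysis follows the methods given above it. Those methods deal with several lesions per patient, not with size.
- Section 9.1.2.1 bases the PET-histology comparison mainly on tumors of at least 0.5 cm³. That restricts the lesion set but leaves size free to vary above the cut.
- No partial correlation, size stratum or model containing both size and Gleason appears in the plan.

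**Simulation.** From the plan: two-sided 0.05 level, Spearman and rank-sum tests. Assumed: 20, 40 or 60 independent lesions; Gleason pattern 3/4/5 in 45/45/10%; 35% of lesions with a high Gleason score; 75% of lesions detected (the plan's per-patient success figure applied per lesion); size-SUV correlation a and size-grade correlation b on a normal latent scale.

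Model, with S the size and E₁, E₂ independent standard normal values:

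- SUV = a·S + √(1 − a²)·E₁
- grade = b·S + √(1 − b²)·E₂, cut into patterns

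SUV therefore has no dependence on grade at a given size. The size-adjusted test uses the partial Spearman coefficient, (r_SUV,G − r_SUV,S · r_G,S) / √[(1 − r²_SUV,S)(1 − r²_G,S)]. There were 3,000 runs per setting. The table shows the percentage of runs with p<0.05:

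| Lesions | a, b | Spearman | Rank-sum, high v low Gleason | Detected v missed on Gleason | Size-adjusted Spearman |
|---|---|---|---|---|---|
| 40 | 0, 0.5 | 5.2 | 5.0 | 4.4 | 5.0 |
| 20 | 0.3, 0.3 | 6.3 | 4.9 | 5.4 | 4.9 |
| 40 | 0.3, 0.3 | 7.5 | 7.1 | 6.0 | 4.5 |
| 20 | 0.5, 0.5 | 15.8 | 12.0 | 9.1 | 5.6 |
| 40 | 0.5, 0.5 | 25.6 | 19.9 | 15.0 | 5.0 |
| 60 | 0.5, 0.5 | 37.7 | 30.8 | 21.4 | 5.6 |
| 40 | 0.7, 0.7 | 76.8 | 67.2 | 48.6 | 6.7 |

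The mean unadjusted SUV-grade coefficient is about 0.07 with both correlations 0.3, 0.21 with both 0.5 and 0.41 with both 0.7. After adjustment it is between about 0.00 and 0.02. More lesions do not help: a larger sample detects the size-driven association more often.

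**Voxel maximum.** The expected maximum of independent standard normal values is about 2.05 SD for 30 voxels and 3.24 SD for 1,000. With assumed voxel noise of 10% of the mean, the ratio of expected SUVmax is (1 + 0.10 × 3.24)/(1 + 0.10 × 2.05) = 1.324/1.205 = 1.10. With 20% noise it is 1.648/1.410 = 1.17. The larger lesion thus reads about 10-17% higher at equal concentration. Voxel counts, noise and independence are assumptions, and correlation between voxels would shrink the effect.

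**The case against.** The strongest reply is that the endpoint is worded as a correlation of SUV with Gleason pattern. That is a marginal association, and an unadjusted Spearman test answers it. In the simulation SUV and grade really are associated marginally, so the 7.5% and 26% are not false positives for that question. They are misleading only if the result is read as grade acting beyond size. This stands, and it is why the planned tests should stay.

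Two stronger readings are tempting. A reader might infer that the plan expects SUV to depend on size. It does not: Sections 1.2 and 12.1 pose this as an open question, and the 5 mm and 0.5 cm³ thresholds only define lesion sets. A reader might also infer that size is an established common cause, so that only the adjusted result counts. The documents give no size-grade correlation and no causal direction. If higher grade leads to larger foci, size lies partly on the path from grade to uptake, and adjustment would remove part of a real grade effect.

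There are also partial safeguards. SUV against size is reported alongside, detected and missed lesions are compared on size as well, and PSMA staining is examined directly. These would make a size effect visible, but they would not show how much of the Gleason association remains once size is allowed for.

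Finally, the data are sparse. With 40 lesions, a 10% share gives about 4 of pattern 5, and 25% missed gives about 10 missed lesions. This limits the model that can be fitted, but it does not rule out a simple one.

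**Conclusion.** The concern holds in a limited form. No planned analysis of SUV or detection against Gleason accounts for lesion size, so an unadjusted association cannot show that uptake tracks grade beyond size.

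The possible size of the problem ranges from negligible to large. It is about 6-8% nominal significance with both correlations at 0.3 (20 or 40 lesions) and about 26% with both at 0.5 and 40 lesions. At 0.5 and above it is substantial in every setting tried. With no size-SUV correlation there is no inflation. All these rates rest on the assumed correlations, lesion counts, grade mix and independence of lesions, none of which the documents supply.

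The point concerns the interpretation of secondary, exploratory results. Calling them hypothesis-generating limits the claim, but it does not separate the two explanations.

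**What to change.** In Section 12.1, keep the Spearman and rank-sum tests as the marginal results and add a size-adjusted exploratory analysis beside them:

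- **Uptake:** a linear model of log SUVmax on Gleason group plus log lesion diameter, with a patient random intercept. Use the plan's two groups (3+4 or lower, 4+3 or higher), because pattern 5 will be sparse. Repeat with SUVmean.
- **Detection:** if the number of missed lesions allows, a logistic GEE of detection on Gleason group plus log diameter. Otherwise report the marginal comparison only, and say so.
- **Reporting:** give estimates with 95% intervals for both versions. State that uptake tracks grade independently of size only if the adjusted result supports it.

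The cost is SAP wording and modest analysis time. Size, Gleason score, SUVmax and SUVmean are already collected, and both model types are already in the plan.

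The statistical price is precision. In an illustration with a true grade effect (0.4 SD of SUV per SD of latent grade, size-SUV coefficient 0.5, size-Gleason correlation 0.5, 40 lesions, all assumed), the adjusted test rejected in about 52% of runs against 89% unadjusted. Part of the 89% is the size effect, and both rates shift with the residual variance assumed. A non-significant adjusted result would therefore not show that grade has no effect. Together with possible over-adjustment if size partly mediates the grade effect, this is why both results should be shown.

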#### 9.1.2 $^{89}\text{Zr}$ -df-IAB2M PET/CT imaging

##### 9.1.2.1 Method of Assessment

PET/CT will be read twice by a nuclear medicine physician. For the first interpretation, the physician will be blinded from clinical history, biopsy results and conventional

imaging modalities. After the initial reading, the nuclear medicine physician will be provided with both the TRUS biopsy results and previously read scans for the repeat PET/CT reading. During each interpretation, the physician will record all abnormal, suspicious areas with higher uptake than adjacent or contralateral background. Each abnormal area will be recorded on a map of the prostate along with maximum standardized uptake value ( $SUV_{max}$ ) and mean standardized uptake value ( $SUV_{mean}$ ).

Subsequently, the accumulation of  $^{89}Zr$ -df-IAB2M will be compared to areas of known PCa foci on histopathology and mpMRI, as described in Section 13. After completion of the histopathology, the PET/CT findings will be compared to histopathology to perform a lesion by lesion analysis with histopathology serving as the reference gold standard. This analysis will primarily include tumors  $\geq 0.5 \text{ cm}^3$  on histopathology, with a secondary assessment of any lesions  $<0.5 \text{ cm}^3$ . Similarly, areas of increased uptake identified on IAB2M, which had been read as suspicious for cancer will be compared to histopathology to determine the underlying pathology (e.g., inflammation, benign prostatic hyperplasia).

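### Lesion-level Spearman and rank-sum tests of SUV against size and Gleason ignore the within-patient correlation that the plan models elsewhere, so their nominal 5% p-values are unreliable

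*Combined protocol and SAP*

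**What the plan says.** Section 12.1, under the primary endpoint's lesion-based analysis, recognises the clustering for SUVmax in tumour and non-tumour regions: "To account for inpatient correlation of multiple lesions, a linear mixed-effects model with a random intercept will be used". Predictive values there use GEE with robust variance.

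The secondary endpoints in the same section do not carry this over:

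- **SUV and size:** "The Spearman-rank correlation coefficient will be used to evaluate the association between SUV and size of the lesion". The bullet on SUV and Gleason pattern uses the same coefficient.
- **SUVmax and grade:** a rank-sum test compares SUVmax "measurements between lesions with low Gleason score (3+4 or lower) and high Gleason score (4+3 or higher").
- **Extra-prostatic extension:** a rank-sum test compares SUVmax "between lesions with and without histopathologically confirmed extra-prostatic extension".
- **SUV and PSA:** "The Spearman-rank correlation coefficient will be used to evaluate the association between SUV and serum PSA levels obtained during screening".
- **Lesions detected or missed on PET:** a rank-sum test on size, PSMA staining and Gleason score, with the added remark "This lesion based analysis will be performed in a similar fashion as described above".

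The section closes with a general rule: "All p-values will be two-sided with statistical significance evaluated at the 0.05 alpha level".

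Several lesions per patient are expected. Section 9.1.2.1 says "the physician will record all abnormal, suspicious areas with higher uptake than adjacent or contralateral background", each with its SUVmax and SUVmean. The histopathology section (9.1.4) calls for a list of every cancer lesion in each patient.

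**The concern.** Spearman and rank-sum p-values treat each lesion as an independent observation. Lesions from one man share his tracer kinetics, body size, scan and general PSMA expression, so their SUVs are likely to be correlated. If size or grade is also partly shared within a man, the data hold less information than the lesion count suggests and p-values come out too small. If high- and low-grade lesions are balanced within men, the comparison is largely within-patient, the plain test overstates the variance, and p-values come out too large. The analyst cannot know beforehand which case applies.

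At stake is how far reported associations of SUV with size, grade or extension can be trusted when they are used to design later studies.

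**Working it through.** **The plan's own figure.** The only calculated figure concerns the patient-level primary proportion: 1.96 × √(0.75 × 0.25 / 20) = 0.190. This reproduces the ±19.0% in sections 12.1 and 12.2. It does not involve lesions and is not in question.

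**Inputs.** From the documents: 20 patients; two-sided 0.05; lesion as unit. Assumed, because the documents give no values: lesions per patient, intra-patient correlation (ICC) of SUV, ICC of size or grade, and share of high-grade lesions.

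**Approximation.** With m lesions per patient, the variance of a lesion-level association under the null is inflated by about 1 + (m − 1) × ICC(covariate) × ICC(SUV). The true error of a nominal 5% test is then about 2 × [1 − Φ(1.96 / √inflation)].

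- m = 3, both ICCs 0.5: inflation 1 + 2 × 0.25 = 1.50; 1.96 / √1.50 = 1.60; error about 11.0%.
- m = 2, both ICCs 0.3: inflation 1.09; 1.96 / √1.09 = 1.88; error about 6.0%.
- Covariate ICC 0: inflation 1; error 5%.

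**Check of the approximation.** Simulation with exactly m lesions per patient, 4,000 null trials per setting and about 30% high grade (grade cut from an underlying normal variable):

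| m | both ICCs | rank-sum | Spearman |
|---|---|---|---|
| 2 | 0.3 | 0.050 | 0.058 |
| 2 | 0.5 | 0.062 | 0.069 |
| 3 | 0.5 | 0.084 | 0.104 |
| 3 | 0.7 | 0.118 | 0.164 |
| 4 | 0.7 | 0.162 | 0.209 |

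**Main simulation.** Lesion counts vary as 1 + Poisson(mean − 1), with mean 2, 2.5 or 3; SUV ICC 0.3, 0.5 or 0.7; 35% high grade; 4,000 null trials per setting. Type I error of the plain tests at nominal 0.05:

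| Setting | SUV v size (Spearman) | SUVmax by grade (rank-sum) |
|---|---|---|
| Size or grade ICC 0.5 | 0.073–0.149 | 0.063–0.111 |
| Size or grade ICC 0 | 0.047–0.054 | 0.044–0.055 |
| One high-grade lesion in every patient | not applicable | 0.011–0.034 |
| Mean 1.5 lesions, ICC 0.5 | 0.065–0.082 | 0.059–0.063 |

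**The two unclear analyses.** If SUV v PSA used lesion-level SUV against a patient-level PSA, the error would be 0.093–0.249. For detected v missed (60% or 75% detected, 3,000 trials per setting), a plain rank-sum test gives 0.060–0.123 at ICC 0.5 and 0.039–0.061 at ICC 0.

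**Extra-prostatic extension.** Not simulated. A comparison of lesions grouped by extension status has the same structure as the Gleason test, but I give no figure for it.

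**Candidate remedies.**

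- Random-intercept model, t on 18 df: 0.039–0.058; at mean 1.5 lesions and ICC 0.5, 0.060–0.066.
- Sign-flip of the 20 patient sums of the rank statistic: 0.047–0.060 for size and Gleason; 0.045–0.061 for detected v missed.
- Cluster-robust rank regression, t on 19 df, 2 to 4 lesions, ICCs 0.3–0.7: 0.060–0.081, still above 5% with 20 clusters.

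**The case against.** The size of the effect rests wholly on assumption. With 2 lesions per patient and both ICCs 0.3, the plain tests are at 5.0% and 5.8%, which is no practical problem. The number that matters is lesions with an SUV. Section 9.1.2.1 records SUV for abnormal PET areas, so a missed lesion may have none. At a mean of 1.5 such lesions the plain Gleason test (0.059–0.063) does as well as the mixed model (0.060–0.066). The Spearman bullets name a coefficient, not a test, and a p-value is inferred from the general 0.05 rule. The extension sentence mixes extra-prostatic sites and lesions, so its unit is not fully clear. The plan calls itself an exploratory pilot with hypothesis-generating estimates, and no decision in it depends on these p-values.

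Most of this is true, and it limits the consequence. It does not remove the inconsistency. The plan accepts the correlation in one lesion analysis and provides for nothing in the next, while setting a significance level for all p-values. The cross-reference to the methods above belongs only to the detected-or-missed bullet and does not say how clustering enters a rank-sum test. The wish for a test that is valid whatever the lesion pattern also stands.

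**Conclusion.** The concern holds. For SUV v size, SUV v Gleason pattern, SUVmax by Gleason group and the between-lesion extension comparison, the named methods do not give valid 5% p-values when lesions cluster within patients.

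The direction is not fixed. With 20 patients, a mean of 2 to 3 lesions and SUV ICC 0.3–0.7, the true error runs from about 1% (rank-sum, one high-grade lesion in every patient) to about 15% (Spearman, size ICC 0.5). It is close to nominal when size or grade is not shared within a patient. The lesion counts, ICCs and grade share are assumptions, and the problem largely fades if few patients have more than one lesion with an SUV.

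SUV v PSA and detected v missed are underspecified rather than wrong. The coefficients and rank comparisons remain usable as descriptions. This should be corrected, but it is secondary: the primary endpoint and its precision are untouched.

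**What to change.** In section 12.1, state the unit of analysis for each secondary test. Then:

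- **SUV v size, SUV v Gleason, extra-prostatic extension:** base inference on the random-intercept model the plan already uses. Regress log SUVmax on size, Gleason group or extension status, with small-sample degrees of freedom. Alternatively, use a patient-level permutation: sum the rank statistic within each patient and flip the signs of the 20 sums at random. Report the plain Spearman and rank-sum statistics as descriptive only. For extension, say also whether the SUV belongs to the extra-prostatic site or to the lesion.
- **SUV v PSA:** one SUV per patient, such as SUVmax of the dominant lesion, after defining dominant, which the plan does not do.
- **Detected v missed:** a clustered rank-sum test or the same sign-flip test, one characteristic at a time.
- Avoid an uncorrected GEE Wald test with several covariates, because 20 clusters are too few for its robust variance.

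The cost is SAP wording and a little programming. P-values will change, often upwards but sometimes downwards. The model replaces a rank measure with one on the log scale, and it can run slightly high (about 6%) when most patients have one lesion. In that setting it gains nothing over the plain Gleason test.
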